### 4.2.2. Objective response rate

The best overall response of patients is defined as the best response designation recorded across all time points from the date of randomisation until disease progression. Overall best responses assessed after the end of study period (last administration + 30 days) will not be reported in the response rate.

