Because worsening in non-target disease cannot be easily quantified, a useful test that can be applied when assessing patients for unequivocal progression is to consider if the increase in overall disease burden on the basis of non-measurable disease is comparable in magnitude to the increase that would be required to declare PD for measurable disease, i.e. an increase in tumour burden representing an additional 73% increase in volume (which is equivalent to a 20% increase diameter in a measurable lesion).

8.1.2.3. *Best overall response*

The best overall response is determined once all the data for the patient are known.

Best overall response is defined as the best response across all time points.

Determination of the overall response in case of presence of target lesions with or without non-target lesions is detailed in Table 21. For patients with non-target lesions only, determination of the overall response is given in Table 22.

Table 21: Time point response: patients with target (+/- non target) disease

Target lesions	Non-Target lesions	New Lesions	Overall response
CR	CR	No	CR
CR	Non-CR / Non-PD	No	PR
CR	Not evaluated	No	PR
PR	Non-PD or not all evaluated	No	PR
SD	Non-PD or not all evaluated	No	SD
Not all evaluated	Non-PD	No	NE
PD	Any	Yes or No	PD
Any	PD	Yes or No	PD
Any	Any	Yes	PD

Non-target tumour lesions including pleural effusion, ascites, lymphangitis and/or bone lesions which are not associated with symptom appearance or symptom worsening will not disqualify a response reported on target lesions if they are not evaluated.

Non target lymph nodes must be evaluated to document a response reported on target lesions.

In those patients who had bone lesions at study entry, non target bone metastases must be evaluated (bone scintigraphy) to document an overall complete response.

Table 22: Time point response: patients with non target disease

Non-Target lesions	New Lesions	Overall response
CR	No	CR
Non-CR / Non-PD	No	Non-CR / Non-PD
Not all evaluated	No	NE
Unequivocal PD	Yes or No	PD
Any	Yes	PD

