9.2. SERIOUS ADVERSE EVENTS

9.2.1. Definition of SAE

A serious adverse event (SAE) includes, but is not necessarily restricted to, any event which:

- results in death (whatever may be the cause),
- is life-threatening,
- results in persistent or significant disability/incapacity,
- requires patient hospitalisation or prolongation of existing hospitalisation,
- is a congenital anomaly or birth defect,
- other events including cancer, overdose, pregnancy and any additional adverse experience or abnormal laboratory values occurring during the study period defined by the protocol as serious or which the investigator considers significant enough or that suggests a significant hazard, contraindications, side effect or precaution will be handled as a serious adverse event.

Any overdose meeting a seriousness criteria should be reported as a SAE as described in § 9.3.

Any pregnancy occurring after patient exposure to study drug, should be reported on the SAE notification form as described in Section 9.4.

Any hospitalisation, or prolongation of hospitalisation due to the circumstances listed below, will not be reported as SAE :

- Planned (as per protocol) medical/surgical procedure, including central venous line (CVL) setting
- Preparation for routine health assessment/procedure (e.g. routine colonoscopy),

- Planned medical/surgical admission (planned prior to entry into study trial, appropriate documentation required),
- Administrative or social reasons (e.g. lack of housing, economic inadequacy, care-giver respite, family circumstances),
- New treatment of the disease within 30 days after the last study drug administration

All deaths occurring while the patient is on study including deaths due to disease progression and deaths within 30 days of last administration of study drug should be notified as SAE.

Unexpected adverse drug reaction is defined as:

An adverse reaction, the nature or severity of which is not consistent with the applicable product information (e.g. Investigator's Brochure for an unapproved investigational product or package insert/summary of product characteristics for an approved product) (see the ICH Guideline for Clinical Safety Data Management: definitions and standards for Expedited Reporting).

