### 4. EFFICACY PARAMETERS

Tumour assessment will be performed according to the revised RECIST guidelines version 1.1 (Therasse P, 2000, Eisenhauer E, 2009). Assessment of all lesions was planned to be carried out at baseline then every 6 weeks (+/- 3 working days) until disease progression, regardless of the timing of the treatment cycles and whatever the treatment administered.

For patients who discontinued the study treatment before the occurrence of disease progression, clinical and radiological assessments of all lesions had to be performed every 6 weeks from time of randomisation until disease progression is documented, then survival information was collected approximately every month for the first 6 months and then every 3 months until death.

For patient who discontinued the study treatment due to PD, survival information was collected approximately every month for the first 6 months and then every 3 months until death.

According to the protocol amendment 11, no follow-up visit will be performed. At the time of this amendment:

- patients under treatment will stop the study at the EOT
- patients under follow-up will stop immediately

The end of study is defined as the date of the last study treatment plus 30 days for the last patient on treatment (EOT of the last patient).

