#### **4.2.4. Duration of response**

The duration of objective response will be measured for responders (CR + PR) from the time that measurement criteria are first met for complete or partial response (whichever status is recorded first), until the first date that recurrent or progressive disease is objectively documented or the date of death due to any cause. The duration of response of patients who are lost to follow-up or reach the time point of analysis without a known record of progression or death will have the duration of response censored at the date of last tumour assessment or last contact date of a follow-up showing no progression, whichever occurred last. For patients who receive a new anti-cancer treatment in the absence of progression, the duration of overall response will be censored at the date of first administration of the new anti-cancer treatment.

Following the protocol amendment 11, the number of censored patient will be higher than expected. The result should be interpreted with cautiously.

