## **15.2.3. Date of first response and date of progression**

### **15.2.3.1. Date of first response**

The date of first response is the first date where CR, or PR is assessed. It can be found in the Tumour assessment form of the eCRF. If for the same Tumour evaluation, the assessments were made at different dates, the maximum of all the dates of assessment of the cycle will be taken into account.

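### Best overall response has no cut-off at the start of a new anti-cancer treatment but duration of response does, so a switch within 30 days of the last dose can give a responder with a negative duration

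*SAP*

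**What the plan says.** **Best response.** SAP 4.2.2 defines it as the best designation "recorded across all time points from the date of randomisation until disease progression". The next sentence adds one limit: "Overall best responses assessed after the end of study period (last administration + 30 days) will not be reported in the response rate". No confirmation is required (SAP 4.2.2, 15.2.2.4), so a single scan is enough. DCR (SAP 4.2.3) is built on the same best response. The protocol definition (Protocol 8.1.2.3) is wider still: "Best overall response is defined as the best response across all time points".

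**First response.** SAP 15.2.3.1: "The date of first response is the first date where CR, or PR is assessed". SAP 4.2.7 measures time to first response from randomisation to the first documented CR or PR. Neither mentions a new treatment.

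**Durations.** For a patient given a new treatment without progression, SAP 4.2.4 states that "the duration of overall response will be censored at the date of first administration of the new anti-cancer treatment". SAP 4.2.5 applies the same rule to duration of disease control. Time to treatment failure (SAP 4.2.6) counts new therapy as a failure.

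**Timing of events.** Protocol 9.2.1 lists "New treatment of the disease within 30 days after the last study drug administration" among the reasons for hospital admission that are not reported as serious adverse events. Scans run every 6 weeks (SAP 4), and the study flow chart also places imaging at the end-of-treatment visit, within 30 days of stopping.

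**The concern.** The start of new therapy closes the patient's record for duration of response but not for response status. The same person can thus be censored on one date and become a responder on a later one.

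Two things are at stake. First, ORR, DCR and time to first response can include findings made while the patient was already on the next line of treatment. The arms may differ in how many patients stop without progression and switch early, so the effect need not cancel. Second, applying SAP 4.2.4 as written can produce a zero or negative duration of response, and the SAP has no rule for handling it.

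**Working it through.** The plan states no figure for this point, so the check applies its own date rules.

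**Inputs**
- Duration in months = ((Date 2 - Date 1) + 1) / 30.4375 (SAP 15.2.1.1). An ordering condition on the two dates is attached. Its operator is unreadable in the text, but the natural meaning is that Date 2 is not before Date 1.
- Duration of response: Date 1 = first CR or PR; Date 2 = first administration of the new treatment, when it starts without progression (SAP 4.2.4).
- Duration of disease control: Date 1 = randomisation (SAP 4.2.5).
- ITT denominators: 230 in arm A and 229 in arm B (Protocol synopsis, number of patients).

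**Step 1: the exposed window.** Further therapy is defined as given after withdrawal from study drug (SAP 6.3), and the response rate ignores assessments later than last administration + 30 days. For the response rate, the gap therefore covers at most the 30 days after the last dose.

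**Step 2: a worked case (days from randomisation).** Last dose day 21, new drug day 30, first PR at the week-6 scan on day 42. The window closes on day 21 + 30 = 51, so the PR counts. Duration of response = (30 - 42) + 1 = -11 days.

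**Step 3: the general pattern**

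| First CR/PR relative to switch | Duration of response (days) |
|---|---|
| Same day | +1 |
| 1 day after | 0 |
| 2 days after | -1 |
| 14 days after | -13 |
| 29 days after (switch day 1, response day 30 after last dose) | -28 (-0.92 months) |

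The last row is the extreme if the 30-day limit also decides who is a responder for duration. That limit is worded for the response rate only. If duration does not inherit it, larger negatives are possible: switch day 1 and response day 42 after the last dose give -40 days (-1.31 months).

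**Step 4: duration of disease control.** It starts at randomisation, so it cannot be negative. It can still be censored before the scan that first documented control.

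**Step 5: effect on the rates.** One reclassified patient changes an arm's ORR or DCR by 1/230 = 0.43 points (arm A) or 1/229 = 0.44 points (arm B). For assumed counts of 1, 2 or 5 in one arm, the change is 0.4, 0.9 or 2.2 points. For scale, Protocol Table 2 gives a 3.9% methotrexate response rate in one second-line or platinum-unsuitable study. Here that would be 0.039 x 229 = 8.9 responders, so one patient is about 11% of the count.

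**Step 6: with the cut-off added.** A first response can no longer fall after the switch, and the shortest duration of response is +1 day (0.03 months).

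**The case against.** **New treatment in the window may already be barred.** Protocol 6.1.1 forbids other anticancer treatment while on study, and Protocol 7.4 runs the treatment period to 30 days after the last dose. Read together, they make the response window coincide with the prohibition. This narrows the exposure but does not close it: Protocol 9.2.1 foresees new treatment in exactly those 30 days, and ITT keeps such patients in the analysis.

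**Several things must coincide.** The patient must stop without progression, switch within 30 days, be scanned after the switch but inside the window, have no earlier response as good, and then show CR or PR (or SD for DCR). This stands, and is why the number is probably small.

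**The scanning rule may not refer to next-line therapy.** The words "regardless of the timing of the treatment cycles and whatever the treatment administered" in SAP 4 could simply mean either study arm. That is fair, so the point does not rest on them. The end-of-treatment imaging and the 6-weekly schedule are enough.

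**Response until progression matches PFS.** SAP 4.2.1 does not censor PFS at new therapy either. That is true, but it does not resolve the conflict between responder status and the censoring in SAP 4.2.4.

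**A late response may still belong to the study drug.** In the worked case the PR comes 12 days after the new drug and 21 days after the last study dose. The documents cannot say which treatment caused it. The defect is the clash of rules, not proven misattribution.

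**These endpoints decide nothing.** SAP 3 calls the secondary efficacy analyses descriptive, and the superiority claim rests on OS. This stands as to weight, although SAP 10.4.2.1 and 10.4.2.2 still list CMH and stratified log-rank comparisons.

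**Conclusion.** The inconsistency is real but narrow. Followed as written, the SAP can count a response or stable disease first seen after a switch. For a first CR or PR two or more days after the switch, it also yields a negative duration of response.

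A reader might infer more than the documents support:
- **That any post-switch response counts until progression.** The 30-day limit in SAP 4.2.2 rules this out for the response rate.
- **That both durations can be negative.** Only duration of response can.
- **That ORR is inflated by a known amount.** No switching or post-switch response rate is given. The only firm size is 0.43 or 0.44 points per patient.
- **That affected patients drop out of the duration table.** The SAP does not say so; it simply has no rule for the invalid value.

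No planned summary table would show how often this occurs, because the analysis of further anti-cancer therapy was deleted (SAP 13); individual efficacy listings remain. OS is unaffected. This is a small correction to secondary endpoints, worth making because it is cheap and the present rule can fail.

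**What to change.** State one rule in SAP 4.2.2, 4.2.3, 4.2.4, 4.2.7 and 15.2.3.1:

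*Only tumour assessments up to and including the earliest of progression, first administration of a new anti-cancer treatment, and last administration + 30 days are used for best overall response, date of first response, and responder or disease-control status for the durations. Patients with no usable post-baseline assessment are NE and remain in the ITT denominator.*

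This uses the cut-off already in SAP 4.2.4 and 4.2.5, and settles whether the 30-day limit also applies to DCR, first response and the durations. It needs no new data, because the start date of the new treatment is already required for that censoring.

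Cost: one sentence and one date filter. ORR and DCR may come out slightly lower, and a few patients may become NE.

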**No confirmation will be needed for the best overall response.**

If a patient had to end the treatment because of progression before the first assessment, he/she will be considered early progressive and the best overall response of the patient will be considered as progression.

The objective Response Rate (ORR) is defined as a percentage of complete and partial responses (CR and PR) observed in the population analysed:

$$ORR = \frac{\sum (\# CR + \# PR)}{N}$$

with:

- # CR = number of patients whose best response is CR,
- # PR = number of patients whose best response is PR,
- N = number of patients qualified for efficacy analysis.

#### 4.2.3. Disease control rate

Disease control rate (DCR) is defined as a percentage of best overall responses CR, PR and SD in the analysed population:

$$DCR = \frac{\sum (\# CR + \# PR + \# SD)}{N}$$

with:

- # CR = number of patients whose best response is CR,
- # PR = number of patients whose best response is PR,
- # SD = number of patients whose best response is SD (SD does not include non CR/non PD),
- N = number of patients qualified for efficacy analysis.

Of note, patients with only non-measurable disease at baseline assigned a best overall response of Non-CR/non-PD, will not be considered as stable and will not be counted as patient having disease control (Table 4-1).

**Table 4-1: Definitions of ORR and DCR**

Type of population analysed	Observed number of best responses
Measurable and/or non-measurable disease	CR PR ORR = (CR + PR)/N SD DCR = (CR + PR + SD)/N Non CR/Non PD* PD NE Total (N)
Measurable disease only	CR PR ORR = (CR + PR)/N SD DCR = (CR + PR + SD)/N PD NE Total (N)

\* for patients with only non measurable disease

#### **4.2.4. Duration of response**

The duration of objective response will be measured for responders (CR + PR) from the time that measurement criteria are first met for complete or partial response (whichever status is recorded first), until the first date that recurrent or progressive disease is objectively documented or the date of death due to any cause. The duration of response of patients who are lost to follow-up or reach the time point of analysis without a known record of progression or death will have the duration of response censored at the date of last tumour assessment or last contact date of a follow-up showing no progression, whichever occurred last. For patients who receive a new anti-cancer treatment in the absence of progression, the duration of overall response will be censored at the date of first administration of the new anti-cancer treatment.

Following the protocol amendment 11, the number of censored patient will be higher than expected. The result should be interpreted with cautiously.

#### **4.2.5. Duration of disease control**

The duration of disease control will be measured for patients with objective response or stable disease, from the date of randomisation until the date of progression or the date of death whatever the cause. The duration of disease control of patients who are lost to follow-up or reach the time point of analysis without a known record of progression or death will have the duration of disease control censored at the date of last tumour assessment or last contact date of a follow-up showing no progression, whichever occurred last. For patients who received a new anti-cancer treatment in the absence of progression, the duration of disease control will be censored at the date of first administration of this new anti-cancer treatment.

Following the protocol amendment 11, the number of censored patient will be higher than expected. The result should be interpreted with cautiously.

#### **4.2.6. Time to treatment failure**

Time-to-treatment failure will be calculated from the date of randomisation up to the date of failure (progression, relapse, death or withdrawal due to adverse event, patient's refusal to continue, lost to follow-up or start of new anti-cancer therapy). Patients who reach the time point of analysis without failure as defined above will have the time to treatment failure censored at the date of last tumour assessment or last contact of a follow-up not showing progression. Patients who discontinued treatment for other reason and who are lost to follow-up will be censored at the date of last contact.

Following the protocol amendment 11, the number of censored patient will be higher than expected. The result should be interpreted with cautiously.

#### **4.2.7. Time to first response**

Time to first response will be calculated among the responders (i.e. CR and PR) from the randomisation date up to the date of first documented CR or PR.

Following the protocol amendment 11, the number of censored patient will be higher than expected. The result should be interpreted with cautiously.

### **5. SAFETY PARAMETERS**

#### **5.1. ADVERSE EVENTS**

Each patient will be assessed for occurrence of adverse events. The CTCAE version 3.0 (publish date 9 Aug 2006) will be used. Adverse events not classified by the CTCAE will also be reported and graded according to their severity: mild (grade 1), moderate (grade 2), severe (grade 3), life-threatening or disabling (grade 4), sudden death (grade 5), not applicable in case of progression or adverse event not gradable according to CTCAE and leading to dose modification (NA).

Treatment Emergent Adverse Events (TEAE) will be considered for analysis of adverse events. A TEAE is defined as any event that first occurred during the treatment period (i.e. from first drug administration date up to last administration date + 30 days) or that “worsened” during that study period. The definition of “worsening” is described below:

- Any increase in the grade (according to CTCAE) compared to baseline sign or symptom, or
- Any sign or symptom becoming serious during the study period, or
- Any sign or symptom requiring a modification of the study drug administration, or
- Any sign or symptom becoming possibly, probably or definitely related to the study drug

An adverse event that meets one of the criteria described above will be considered as TEAE and reported in the analyses for the remainder of the study, even if the TEAE downgrades to baseline situation.

Baseline situation of the pre-treatment adverse events will be determined by using:

- the worst grade of the adverse events during the pre-study period (within 2 weeks prior to treatment),
- the seriousness of the event during the pre-study period,

This situation will be used as comparator to determine whether an existing adverse event during study period becomes treatment-emergent.

The adverse events will be classified using the Medical Dictionary for Regulatory Activities (MedDRA). The implementation of this international terminology in the Oracle Clinical® database will be performed using the available version of MedDRA (Version 19.0). Each description of the toxicity (verbatim) will be associated with the five following items:

- System Organ Class (SOC),
- High Level Group Term (HLGT),
- High Level Term (HLT),
- Preferred Term (PT),
- Lowest Level Term (LLT).

Two sets of events will be considered:

- all adverse events regardless of relationship to treatment,
- the adverse events that are possibly, probably or definitely related to treatment,

*Of note, if the causality is missing, the AE will be considered as related to study treatment*

A patient will be evaluable for non-haematological toxicity if at least one drop of any treatment was given and the toxicity has been assessed by the investigator. The patient will be analysed in the treatment arm he/she was effectively treated.

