### **5.1.2. Serious Adverse Event**

A serious adverse event (SAE) includes, but is not necessarily restricted to, any event which:

- Results in death (whatever may be the cause),
- Is life-threatening,
- Results in persistent or significant disability/incapacity,
- Requires patient hospitalisation or prolongation of existing hospitalisation,

- Is a congenital anomaly or birth defect,
- Other events including cancer, overdosage, pregnancy and any additional adverse experience or abnormal laboratory values occurring during the study period defined by the protocol as serious or which the investigator considers significant enough or that suggests a significant hazard, contraindications, side effect or precaution will be handled as a serious adverse event.

Any overdosage meeting seriousness criteria should be reported as a SAE.

Any pregnancy occurring after patient exposure to study drug(s), should be reported on the SAE notification form.

All deaths occurring while the patient is on study including deaths due to disease progression and deaths within 30 days of last administration of study drug should be notified as SAE.

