### 11.2. ADVERSE EVENTS

#### 11.2.1. All adverse events

The incidences of the treatment-emergent adverse events (TEAE) as defined in 5.1, graded according to CTCAE version 3.0 will be presented using the MedDRA SOC and PT defined during the MedDRA coding process.

A summary table will provide by treatment arm the following:

On treatment deaths

Patients with at least one AE

Patients with at least one TEAE

Patients with at least one SAE

Patients with at least one related TEAE

Patients with at least one related TESAE

Patients with at least one TEAE leading to discontinuation

Patients with at least one TEAE requiring dose interruption and/or adjustment

Patients with at least one TEAE requiring dose interruption

Patients with at least one TEAE requiring dose adjustment

Patients with at least one TEAE requiring additional therapy

Cycles with at least one AE

Cycles with at least one TEAE

For all these items, the overall incidence, the incidence of grade 3/4, the incidence of grade 5 and the incidence of grade NA will be provided.

Overall incidences per patient will be depicted as well as the incidence of non related and related toxicities only. An analysis will also present the CTCAE grade presented for each SOC and PT per patient according to the relationship with study treatment.

Of note, some laboratory toxicities will be presented in the non-haematological adverse event tables when reported as adverse events as per study completion guidelines. However, biochemical and haematological event should be interpreted from the tables described in section 5.1

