### **11.2.3. Serious adverse events**

The number of patients with at least one SAE, one related (suspected and insufficiently documented) SAE, number of SAEs, number of related SAEs will be tabulated. Incidences of SAEs by SOC and PT will be presented according to the relationship with study treatment.

A listing of the serious toxicities will also be provided with the following variables: patient number, cycle number, seriousness, CTCAE grade, relationship to treatment, date of onset, date ceased and significant consequences.

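### The all-causality TEAE, SAE and TEAE-discontinuation rows include progression deaths and any progression entered as an adverse event, so they mix treatment failure with toxicity

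*SAP*

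**What the plan says.** SAP 5.1 grades events by CTCAE version 3.0 and adds a scale for the rest: "Adverse events not classified by the CTCAE will also be reported and graded according to their severity". That scale runs from mild (grade 1) to grade 4 and ends with "sudden death (grade 5), not applicable in case of progression or adverse event not gradable according to CTCAE and leading to dose modification (NA". Grade NA thus covers two different things, progression and ungradable events that altered dosing.

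The same section sets the window: "A TEAE is defined as any event that first occurred during the treatment period", meaning first dose to last dose plus 30 days, or an event that worsened in that time. It makes no exception for progression.

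SAP 5.1.2, like protocol 9.2.1, requires SAE notification for "All deaths occurring while the patient is on study including deaths due to disease progression", and for deaths within 30 days of the last dose.

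The summary table in SAP 11.2.1 counts, by arm, patients with at least one TEAE, patients with at least one SAE, and "Patients with at least one TEAE leading to discontinuation". For every row, the overall incidence is given and "the incidence of grade 3/4, the incidence of grade 5 and the incidence of grade NA will be provided". For SAEs, SAP 11.2.3 adds: "Incidences of SAEs by SOC and PT will be presented according to the relationship with study treatment". None of these rows excludes progression or progression deaths.

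**The concern.** Assessing safety in both arms is a secondary objective (protocol section 2). After the last amendment the safety analyses stay as planned (protocol 11.5.1), and SAP section 13 says that adverse-event summary tables were added in this version. These rows are therefore likely to be read as the headline toxicity comparison between the combination and methotrexate alone.

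A row that counts progression as well as toxicity is no longer a toxicity rate. If progression is equally common in both arms, the toxicity difference shrinks. If it differs, the arm with poorer tumour control collects extra events, and the row moves against that arm for a reason unrelated to drug safety.

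The grade 5 wording raises a smaller issue. A reader of the grade 5 column expects fatal events, but for events outside the CTCAE the scale names only sudden death.

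**Working it through.** The plan states no figure on this point, so the check is mainly a reading of the rules side by side, followed by an illustration.

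**1. What certainly enters the rows.** Progression deaths are SAEs by explicit rule, so they enter the any-SAE row and, if they fall in the treatment window, meet the TEAE definition.

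**2. What may enter.** Non-fatal progression has a grading code in the adverse-event scale, and an NA incidence is reported for every summary row. The documents do not say whether each progression is recorded on the adverse-event form. Protocol 7.6 requires treatment to stop at progression, so an entry of this kind would tend to fall in the TEAE-discontinuation row.

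**3. Whether other output allows it to be removed.**
- The NA column cannot isolate progression because the code is mixed. The SAE form (protocol Appendix 5) asks for grades 1 to 5 only, so a fatal progression could appear as grade 5 or as NA.
- SOC and PT lines may show a progression term, but patient counts cannot be corrected by subtraction. The number with toxicity or progression equals the number with toxicity plus the number with progression minus the number with both, and no table gives the overlap.
- Related-event tables help only in part. Causality is judged open-label, missing causality counts as related (end of SAP 5.1), and insufficiently documented SAEs count as related (SAP 11.2.3).

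**4. Illustration for the SAE row (all rates assumed).** Let t be the SAE rate without progression and p the progression-SAE rate, taken as independent. Reported rate = 1 − (1 − t)(1 − p). Take t = 40% in arm A and 25% in arm B, a true difference of 15 points.

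| p, arm A | p, arm B | Arm A reported | Arm B reported | Difference |
|---|---|---|---|---|
| 10% | 15% | 1 − 0.60 × 0.90 = 46% | 1 − 0.75 × 0.85 = 36.25% | 9.75 points |
| 10% | 20% | 46% | 1 − 0.75 × 0.80 = 40% | 6 points |
| 15% | 15% | 1 − 0.60 × 0.85 = 49% | 36.25% | 12.75 points |

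With equal p the difference is simply (1 − p) times the true one: 0.85 × 15 = 12.75.

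**5. Illustration for the TEAE-discontinuation row (an extreme case).** Suppose every progression were entered as an adverse event leading to discontinuation. For arm A, p = 1 − 61% = 39%, from the expected 6-week non-progression rate in protocol 11.5.6.2. No 6-week control rate is given. As a stand-in, p for arm B is 1 minus the disease control rates of 48.0% and 27.0% (highest and lowest of the three post-platinum or second-line methotrexate rows in protocol Table 2), that is 52% to 73%. Toxicity discontinuation rates are assumed.
- With 10% in both arms, arm A shows 1 − 0.90 × 0.61 = 45.1%. Arm B shows 1 − 0.90 × 0.48 = 56.8% to 1 − 0.90 × 0.27 = 75.7%. A true difference of 0 appears as 11.7 to 30.6 points in favour of arm A.
- With 20% against 10%, arm A shows 1 − 0.80 × 0.61 = 51.2%. A true excess of 10 points in arm A appears as a deficit of 5.6 to 24.5 points.
- With 39% progression in both arms, the 10-point excess appears as 0.61 × 10 = 6.1 points.

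At the other end, if no progression is entered as an adverse event leading to discontinuation, this row is undisturbed.

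**6. Grade 5.** SAP 15.2.4.3 defines a toxic death as one caused by a related adverse event, with no condition that it be sudden. SAP 11.2.1 reports grade 5 incidence separately. For an event outside the CTCAE, a fatal outcome that was not sudden fits the toxic-death definition but matches no fatal grade in the scale.

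**The case against.** The strongest reply is that the grading sentence sets progression beside adverse event and may be meant to keep the two apart. No passage tells sites to enter progression on the adverse-event form, and protocol 7.6 has a progressing patient reported as a progression. This stands as far as non-fatal progression goes: whether and how often it is entered is not settled. It does not reach progression deaths, which are SAEs by explicit rule.

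The plan also separates progression in several places:
- The discontinuation reasons in SAP 9.1.1 list adverse event and progressive disease apart, and SAP 15.2.5.1 codes a death for progression as Progression.
- SAP 11.2.4 splits deaths by cause.
- The special-interest events (SAP 5.1.1 and Appendix 3) come from a fixed list with no progression term and are tabulated regardless of relationship.
- Haematological and biochemical toxicities are graded from laboratory values.

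All of this stands. These outputs are sound, and they give an all-causality toxicity comparison that does not depend on open-label causality. They do not correct the three summary rows.

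It is also fair to say that all-causality SAE tables include every cause by design, that the SAP specifies no between-arm safety test, and that individual listings would allow a hand count. This limits the consequence to how descriptive rates are read.

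**Conclusion.** The point holds as a minor-to-moderate reporting correction. The any-TEAE, any-SAE and TEAE-discontinuation rows include progression deaths and any progression entered as an adverse event, and nothing in the plan lets a reader recover the toxicity-only count from the tables. The primary overall survival analysis is unaffected.

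The size is unknown. The figures above rest on assumed rates and independence, and those for discontinuation also assume that every progression is entered as an adverse event.

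Three stronger conclusions that a reader might infer are not supported:
- That every progression is counted as an adverse event, or that non-fatal progression is in itself an SAE. The documents do not say so.
- That the rows will understate the toxicity of the combination by a known amount. This needs a known arm difference in progression. The documents give none, and they report a very low probability of showing a significant survival benefit.
- That grade 5 means sudden death throughout. The phrase governs only events not classified by the CTCAE. Nor does the SAP say that a non-sudden fatal event takes grade 4; it simply assigns no fatal grade.

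**What to change.** 1. In SAP 5.1, give progression its own code, apart from ungradable events that led to dose modification.
2. In SAP 11.2.1 and 11.2.3 (tables 12_2_1 and 12_2_2_3a), show the TEAE, SAE and TEAE-leading-to-discontinuation rows with and without disease-progression events, including progression deaths. Use the rows without progression when describing toxicity by arm.
3. In the scale for events outside the CTCAE, reword grade 5 as *death caused by the adverse event*.

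The cost is a few lines of SAP wording and one extra set of rows. Events are already coded in MedDRA and deaths already carry a cause, so no new data are needed.
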